3.5.2 Secondary Efficacy Analyses

The secondary efficacy analyses will be performed in a similar way to the primary analysis, which include:

- Comparison of change and percent change from Baseline to each schedule post-Baseline visit in AGT between ISIS 757456 80 mg group and placebo group in PPS and FAS
- Comparison of change from Baseline to each schedule post-Baseline visit in in-clinic SBP and DBP between ISIS 757456 80 mg group and placebo group in PPS and FAS. Subsequent SBP and DBP measurements will be completely removed from this analysis once the subjects received first administration of antihypertensive therapy during the study.

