 - v. carvedilol (≤ 25 mg b.i.d.)
 - vi. labetalol (≤ 200 mg b.i.d.)
 - vii. metoprolol (≤ 100 mg q.d.)
 - viii. nadolol (≤ 40 mg q.d.)

- ix. nebivolol (≤ 10 mg q.d.)
 - x. propranolol (≤ 120 mg q.d.)
 - xi. pindolol (≤ 5 mg b.i.d.)
- b. calcium channel blocker or
 - c. diuretic
10. At Screening, the average office seated BP must be within ≤ 140 mmHg systolic and ≤ 90 mmHg diastolic. The average is to be derived from 3 assessments taken within 10 minutes. Up to 2 additional tests allowed in order to qualify
 11. On Study Day -7, the average office seated systolic blood pressure (SBP) must be within the following ranges with $> 140 - \leq 165$ mmHg. The average is to be derived from 3 assessments taken within 10 minutes. Up to 2 additional tests allowed for eligibility purposes
 12. In the opinion of the Investigator, the subject could be safely withdrawn from antihypertensive therapy for at least 12 weeks
 13. Agree to conduct at home BP and HR monitoring (in triplicate using study provided device) thrice weekly and document the average of the triplicate measurements assessed on a day in the patient diary
 14. Agree to abstain from alcoholic beverages for at least 24 hours prior to clinic visits
 15. Agree to maintain adequate hydration and current diet regimen
 16. Agree to abstain from smoking, exercise, and caffeine use 30 minutes prior to blood pressure measurements.

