Appendix A Schedule of Procedures

Study Week	Screen	Run-In	WO			Treatment (6 Weeks)						Post-Treatment Evaluation Period (13 Weeks)					
		Wk -3	Wk -2	Wk -1	Wk1	Wk 2	Wk3	Wk4	Wk5	Wk6	Wk7	Wk8	Wk10	Wk12	Wk16	Wk19	
Study Day	D-42 to D-22	D-21	D-14	D-7	D1	D3	D8	D15	D22	D29	D36	Treatment Early Term ⁹ /D43	D50	D64	D78	D106	PT Early Term ⁹ /D127
Visit Window	N/A		± 1	± 1		+2	+2	± 2	± 2	± 2	± 2	± 2	± 2	± 2	± 5	± 5	± 5
Scheduled Visit #	1	2	3	4	5	6	7	8	9	10	11	12	13	14	15	16	17
Informed Consent	X																
Inclusion/Exclusion	X			X													
Medical History	X																
CVD Risk Factors	X																
Body Weight and Height ⁸	X				X							X					X
Physical Exam ¹	X				X							X					X
ECG (12-Lead)	X				X ^c						X ^c	X					
Vital Signs (clinic) ²	X	X	X	X	X ^a	X ^a	X ^a	X ^a	X ^a	X ^a	X ^a	X	X	X	X	X	X
Home BP/HR ²		X	X	X	X	X	X	X	X	X	X	X	X	X	X	X	X
HIV, HepB & C	X																
FSH ³	X																
Pregnancy Test ⁴	X																
Chemistry Panel (Fasting) ^{7, 11}	X				X ^a	X ^a	X ^a	X ^a	X ^a	X ^a	X ^a	X	X	X	X	X	X
Renal Urine Biomarkers	X				X ^a	X ^a	X ^a	X ^a	X ^a	X ^a	X ^a	X	X	X	X	X	X
TSH, FT3, FT4	X																
Hematology ⁷	X				X ^a	X ^a	X ^a	X ^a	X ^a	X ^a	X ^a	X	X	X	X	X	X
Urinalysis ¹⁰	X				X ^a	X ^a	X ^a	X ^a	X ^a	X ^a	X ^a	X	X	X	X	X	X
Angiotensinogen	X			X	X ^a	X ^a	X ^a	X ^a	X ^a	X ^a	X ^a	X	X	X	X	X	X

ISIS 757456-CS2
 Protocol

CONFIDENTIAL

Amendment 1
 29 March 2019

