1.2.2 Secondary Objective(s)

- To evaluate the effect of ISIS 757456 on in-clinic systolic blood pressure over time in Treatment and Post-Treatment Periods

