3 ANALYSIS PLAN

3.1 General Overview of Analyses

Descriptive summary statistics including number of subjects, mean, median, standard deviation, standard error of mean, 25th percentile, 75th percentile, minimum, and maximum for continuous variables, and counts and percentages for categorical variables will be used to summarize most data. All statistical tests will be conducted using 2-sided tests with 5% Type I error rate unless otherwise stated.

[figure not shown]
PK parameters will be summarized using include number of subjects, mean, standard deviation, coefficient of variation (CV), geometric mean, median, minimum, and maximum.

Baseline definition:

The baseline for plasma AGT will be define as the average of all values on or after Study Day -7 and prior to the first dose of Study Drug. The baseline for all other assessments will be defined as the last non-missing measurement prior to the first dose, unless otherwise specified.

Analytical visits:

Data will be summarized using the visit labels provided in the data. Multiple results with the same visit label will be averaged. Results with visit labels as "Unscheduled" will not be included in the by-visit summary tables and figures except for determining baseline and the analysis of confirmed ALT/AST category (see section 3.7.3) but will be presented in data listings.

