3.5 Efficacy Analysis

3.5.1 Primary Efficacy Analysis

The primary analysis will be the comparison of percent change from Baseline to Study Week 7 (Study Day 43) in plasma AGT between ISIS 757456 80 mg group and placebo group in PPS. The data will be analyzed using analysis of variance (ANOVA) with treatment and randomization stratification factor (screening AGT concentration) as independent variables. The normality assumption for the ANOVA model will be assessed by the Shapiro-Wilks test on the residuals. In the case data departs substantially from normality, the nonparametric van Elteren test will be employed instead.

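### Change in in-clinic SBP and DBP is, on the natural reading, not adjusted for baseline BP; the analysis is valid but usually less precise than the collected data allow

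*Combined protocol and SAP*

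**What the plan says.** SAP 3.5.2 states that "The secondary efficacy analyses will be performed in a similar way to the primary analysis" and then lists "Comparison of change from Baseline to each schedule post-Baseline visit in in-clinic SBP and DBP", in both the PPS and the FAS. Protocol 10.6.3 has the same arrangement. The model being carried over is in SAP 3.5.1: "The data will be analyzed using analysis of variance (ANOVA) with treatment and randomization stratification factor (screening AGT concentration) as independent variables". Its fallback is: "In the case data departs substantially from normality, the nonparametric van Elteren test will be employed instead". Neither method contains a baseline BP term, and no readable section of either document adds one.

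For BP, SAP 3.1 sets the baseline rule: "The baseline for all other assessments will be defined as the last non-missing measurement prior to the first dose". Protocol Appendix A schedules a pre-dose clinic vital-signs reading on Day 1 and 12 clinic visits after it (Days 3 to 127). The entry restriction applies one week earlier: "On Study Day -7, the average office seated systolic blood pressure (SBP) must be within the following ranges", the range being above 140 and up to 165 mmHg (Protocol 5.1, criterion 11). Randomisation is stratified on screening AGT only (Protocol 10.1).

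The single secondary objective is "To evaluate the effect of ISIS 757456 on in-clinic systolic blood pressure over time in Treatment and Post-Treatment Periods" (SAP 1.2.2).

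**The concern.** A change score subtracts the whole baseline value. When baseline and follow-up are imperfectly correlated, this usually subtracts too much: the noise in the baseline reading enters the outcome, and subjects who start high tend to fall further whatever they receive. Putting baseline in the model removes that component. BP is not a stratification factor either, so with 20 versus 10 subjects neither the design nor the analysis deals with a chance difference in starting BP.

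At stake is the precision of the estimated SBP effect, and how far one realised baseline imbalance can move it. The covariate needed is already collected.

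**Working it through.** **Inputs from the documents.** About 30 subjects at 2:1 (Protocol 3.1 and 3.3): 30 x 2/3 = 20 active and 30 x 1/3 = 10 placebo. Two-sided 5% tests (SAP 3.1). Baseline rule, Day 1 reading and Day -7 window as above. The readable text gives no BP effect size, SD or correlation, so there is no figure of the plan to reproduce and every BP input below is an assumption.

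**Formulas.** Let sb and sf be the baseline and follow-up SDs and rho their correlation.

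- Variance of a change score: sb² + sf² − 2·rho·sb·sf
- ANCOVA residual variance: sf²(1 − rho²)
- Variance ratio: the second divided by the first. Below 1 favours ANCOVA.
- Cost of estimating one covariate: 1 + 1/(N − 5), which is 1 + 1/25 = 1.04 at N=30 and 1 + 1/15 = 1.067 at N=20

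**Step 1: equal SDs.** The ratio reduces to (1 + rho)/2. Half-widths are for an assumed SD of 12 mmHg, 20 versus 10.

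| rho | ratio | x 1.04 | 95% CI half-width, ANOVA to ANCOVA (mmHg) |
|---|---|---|---|
| 0.3 | 0.65 | 0.68 | 11.3 to 9.3 |
| 0.5 | 0.75 | 0.78 | 9.5 to 8.4 |
| 0.7 | 0.85 | 0.88 | 7.4 to 7.0 |
| 0.9 | 0.95 | 0.99 | 4.3 to 4.2 |

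Worked at rho 0.5: the change SD is 12·√(2 × 0.5) = 12 and the SE is 12·√(1/20 + 1/10) = 4.65. Multiplying by t(27 df) = 2.05 gives 9.5. For ANCOVA the SD is 12·√0.75 = 10.39 and the SE 4.02. Multiplying by √1.04 and by t(26 df) = 2.06 gives 8.4. Simulation with the AGT stratum in both models (4,000 trials per setting) gave 9.4 and 8.4.

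**Step 2: baseline SD well below follow-up SD.** Follow-up SD is 12.

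| sb | rho | ratio | x 1.04 |
|---|---|---|---|
| 7 | 0.5 | 108/109 = 0.99 | 1.03 |
| 7 | 0.7 | 73.4/75.4 = 0.97 | 1.01 |
| 8 | 0.5 | 108/112 = 0.96 | 1.00 |
| 8 | 0.7 | 73.4/73.6 = 1.00 | 1.04 |

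Here the regression slope on baseline (rho·sf/sb) is close to 1, so the plain change score is already nearly optimal.

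**Step 3: does the Day -7 window put SBP in that unfavourable region?** The analysis baseline is the later Day 1 reading, which still varies and regresses. A grid of 36 settings applied the window at Day -7 and took a separate Day 1 baseline: post-washout mean 145 or 150 mmHg, between-person SD 8/10/12, visit noise SD 5/7/9, drift SD 4/8. It gave sb 7.8-12.3, sf 8.8-14.7 and rho 0.29-0.62.

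- SBP at N=30: ratio 0.73-0.97, a 3-27% reduction (median 14%).
- SBP at N=20: ratio 0.75-0.99, a 1-25% reduction.
- DBP, 18 settings (between-person SD 6/8/10, noise 4/5/6, drift 3/5, selected only through SBP with true-value correlation 0.6): 1-21% reduction (median 9%) at N=30, and from 19% reduction to 2% loss at N=20.

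**Step 4: chance imbalance.** A one-SE baseline difference is sb·√(1/20 + 1/10) = 0.387·sb. It shifts the change-score contrast by (1 − rho·sf/sb) times that, or 0.387·(sb − rho·sf). At rho 0.5 this is 1.9 mmHg for SDs 10 and 10, 1.5 for 10 and 12, 0.8 for 8 and 12, and 0.4 for 7 and 12.

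**Step 5: validity and power.** In simulated 20 versus 10 trials with two strata (five of the SBP settings, normal or heavy-tailed noise, 4,000 trials each), bias was at most 0.12 mmHg for both estimators, and rejection under no effect lay between 3.9% and 5.9%. For an assumed 8 mmHg difference, power was 26.4-68.6% with ANOVA and 31.0-74.7% with ANCOVA, a gain of 4-9 points.

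**The case against.** The strongest reply is that this is only efficiency on a secondary endpoint. The primary endpoint is AGT at Day 43, the readable sample-size rationale (Protocol 3.3) is safety and tolerability, and no readable text claims power for BP. A gain of 4-9 points does not change what about 30 subjects can show. All of that stands, and it limits the weight of the point.

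The size is also wholly assumed. The SBP grid gives both arms the same spread and ignores the two extra Day -7 tests that Protocol 5.1 allows. Adding between-subject drug response in the active arm lowers the median gain from 14% to about 12% (response SD 8 mmHg) or 11% (SD 10). The power figures come from a selection of settings. The direction survives; the amount is modest. DBP change, moreover, appears only among the listed analyses, not in the secondary objective or endpoints, so the case rests mainly on SBP.

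Three stronger readings are tempting and not supported:

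- **That the plan is biased or inflates Type I error by omitting baseline.** Randomisation protects the unadjusted comparison, and the simulations agree.
- **That the plan rules out a baseline term.** Asking for an analysis similar to the primary one leaves the BP model unstated; it does not expressly exclude the term.
- **That a switch to van Elteren makes adjustment inconsistent between visits.** As written, neither method uses baseline BP, so there is no adjustment to lose.

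**Conclusion.** The point holds as a matter of precision. On the natural reading, the in-clinic BP comparisons omit a covariate that is already measured. Omitting it leaves them unbiased over repeated randomisations and at their 5% level, but usually less precise than they could be, with chance baseline imbalance unadjusted.

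Under the assumed settings that respect the entry window, no SBP setting lost precision at N=30 or N=20. Outside that grid, with baseline SD far below follow-up SD, adjustment can lose a few percent. These sizes depend on assumed SDs and correlations and on N between 20 and 30. The analysed number may fall over time, because SAP 3.5.2 removes BP values once antihypertensive therapy starts and SAP 3.3.2 imputes nothing. Any effect of that removal on the comparison is a separate question, not assessed here.

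This is a cheap improvement to a sound analysis. The AGT and biomarker analyses are outside it.

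**What to change.** In SAP 3.5.2, state the BP model outright: ANCOVA for change in in-clinic SBP, and separately for DBP, at each scheduled visit, with treatment, AGT stratum and that parameter's own continuous baseline (SBP for SBP, DBP for DBP). The quantity estimated, a difference in mean change, stays the same.

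The cost is one degree of freedom, about 4% in variance at 30 subjects and 7% at 20, with the small possible net loss noted above. No new data are needed. Protocol 10.6.3 has the same general wording; aligning it can wait for an amendment made for other reasons, since Protocol 12.1 requires investigator agreement and notification of the regulator and IRB for any amendment.

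A baseline-adjusted rank test, such as stratified rank ANCOVA, in place of van Elteren for these BP endpoints is optional. With heavy-tailed noise it gained only 1-5 points of power in the simulations and, like van Elteren, it gives a test without an effect estimate.

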1.1.2. Secondary Objectives

- To evaluate the effect of ISIS 757456 on in-clinic systolic blood pressure over time in Treatment and Post-Treatment Periods

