3. EXPERIMENTAL PLAN

3.1. Study Design

This will be a Phase 2, double-blind, randomized, placebo-controlled study of ISIS 757456 conducted in mild hypertensive subjects on an ACEi/ARB and an additional hypertensive medication (see Section 5.1 Inclusion Criteria). Subjects will be stratified based on a screening plasma AGT concentration ($\leq 30 \mu\text{g/mL}$ vs. $> 30 \mu\text{g/mL}$) and randomized in a 2:1 ratio to receive a once-weekly SC treatment and an additional loading dose on Study Day 3 with either ISIS 757456 80 mg or placebo for 6 weeks (See [Study Design and Treatment Schema](#)).

All subjects will complete a 13-week Post-Treatment Period. In the Post-Treatment Period, should a subject's sitting BP on home monitoring exceed 140 mmHg systolic or 100 mmHg diastolic on 2 consecutive days (confirmed by triplicate measurement at the Study Center), the subject's initial HTN medication(s) may be added back per Investigator and Sponsor Medical Monitor judgment and the subject will continue to be followed per protocol in the study.

Refer to Section 8.1 for additional details.

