3.3. Number of Subjects

Approximately 30 subjects are planned to be enrolled in this study.

The 80 mg once-weekly dose is designed to assess the safety, tolerability, and efficacy of Study Drug (ISIS 757456 or placebo) given over a 6-week period. An additional loading dose will be given on Study Day 3. The sample size was selected to ensure that the safety and tolerability of ISIS 757456 will be adequately assessed while minimizing unnecessary subject exposure.

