2. Prior to Study Day 64 in the Post-Treatment Period or in the Washout Period, should a subject's BPM exceed 170 mmHg (systolic) or 110 mmHg (diastolic) a second measurement must be done within a 30-minute period. If the subject's BP is $>$ 170 mmHg (systolic) or $>$ 110 mmHg (diastolic) within the 30-minute period, an additional BP measurement should be taken within 48 hours at the Study Center, regardless of whether the initial BP measurements were taken in clinic or at home. If the subject then experiences an additional BP measurement $>$ 170 mmHg (systolic) or $>$ 110 mmHg (diastolic) (confirmed by triplicate measurement at the Study Center), they will then be withdrawn from further blinded, randomized treatment. The subject's pre-study antihypertensive medication(s) may be added back per Investigator and Sponsor Medical Monitor judgement. The subject will continue to be followed per protocol in the study. Follow-up for subjects that screen fail due to blood pressure inclusion criteria (see Section 5.1) will not be necessary.
3. On or after Study Day 64 in the Post-Treatment Period, should a subject's BPM exceed 140 mmHg (systolic) or 90 mmHg (diastolic) a second measurement must be done within a 30-minute period. If the subject's BP is $>$ 140 mmHg (systolic) or $>$ 90 mmHg (diastolic) within the 30-minute period, an additional BP measurement should be taken within 48 hours at the Study Center, regardless of whether the initial BP measurements were taken in clinic or at home. If the subject then experiences an additional BP measurement $>$ 140 mmHg (systolic) or $>$ 90 mmHg (diastolic) (confirmed by triplicate measurement at the Study Center), the subject's pre-study antihypertensive medication(s) may be added back per Investigator and Sponsor Medical Monitor judgement. The subject will continue to be followed per protocol in the study.

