3.3.2 Handling of Missing Data

Missing values will not be imputed.

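### Deleting blood pressure after add-back turns the Day 78, 106 and 127 SBP comparisons into comparisons of outcome-selected survivors, because the Day 64 systolic trigger equals the entry floor

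*Combined protocol and SAP*

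**What the plan says.** The only secondary objective (protocol 1.1.2) is: "To evaluate the effect of ISIS 757456 on in-clinic systolic blood pressure over time in Treatment and Post-Treatment Periods". The Post-Treatment visits are Days 43, 50, 64, 78, 106 and 127 (protocol 3.4.4).

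- **Entry.** Inclusion criterion 11: "On Study Day -7, the average office seated systolic blood pressure (SBP) must be within the following ranges", namely above 140 and up to 165 mmHg. Subjects are then off all antihypertensives.
- **Add-back.** Protocol 8.5.3, item 3, begins: "On or after Study Day 64 in the Post-Treatment Period, should a subject's BPM exceed 140 mmHg (systolic) or 90 mmHg (diastolic". After a repeat within 30 minutes and a Study Center confirmation within 48 hours, pre-study drugs may be returned at the judgement of the Investigator and Sponsor Medical Monitor. Before Day 64 the thresholds are 170 and 110. Subjects stay in follow-up.
- **Analysis.** SAP 3.5.2 compares change in SBP and DBP at every scheduled visit in the same way as the primary endpoint (ANOVA with treatment and AGT stratum), in both PPS and FAS. It adds: "Subsequent SBP and DBP measurements will be completely removed from this analysis once the subjects received first administration of antihypertensive therapy during the study". SAP 3.3.2: "Missing values will not be imputed".
- **Analysis sets.** The PPS bars antihypertensives only up to Day 43, so it does not deal with later add-back.

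Protocol 3.1 and SAP 1.1 state a different add-back rule: home BP above 140 systolic or 100 diastolic on two consecutive days, for the whole Post-Treatment Period, with no change at Day 64.

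**The concern.** The systolic add-back threshold from Day 64 is the floor that every subject had to exceed to enter. Those who stay in the analysis at Days 78 to 127 are mainly subjects whose SBP fell to about 140 or below, or whose physician chose not to act. Presence in the analysis thus depends on the outcome and, if the drug lowers SBP, on treatment.

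Three things follow. Mean change among survivors is too favourable in each arm. The between-arm difference tends to shrink, because placebo loses the larger share of its subjects. The late comparison may rest on a handful of placebo subjects. These are the visits from which a reader would judge whether the SBP effect lasts after dosing stops.

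**Working it through.** **Inputs from the documents.** "Approximately 30 subjects are planned to be enrolled in this study" (protocol 3.3), "randomized in a 2:1 ratio to receive a once-weekly SC treatment" (protocol 3.1): 30 × 2/3 = 20 active and 30 × 1/3 = 10 placebo. Testing: "All statistical tests will be conducted using 2-sided tests with 5% Type I error rate unless otherwise stated" (SAP 3.1). SBP baseline is the last value before first dose. The public text gives no SBP effect size, SD, power or add-back share, so there is no planned figure to reproduce.

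**Step 1: one subject, by hand.** Assume a visit SD of 6 mmHg and a trigger that needs two independent readings above 140. For true SBP m, the chance of a confirmed trigger at a visit is Φ((m − 140)/6)².

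- Unchanged subject, m = 146: Φ(1.00)² = 0.841² = 0.708.
- Same subject lowered by 8, m = 138: Φ(−0.33)² = 0.369² = 0.136.

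If a share p of confirmed triggers leads to add-back, the chance of still being analysed at Day 127, after chances at Days 64, 78 and 106, is (1 − p × trigger chance)³:

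| p | Unchanged | Lowered by 8 |
|---|---|---|
| 10% | (1 − 0.071)³ = 0.80 | (1 − 0.014)³ = 0.96 |
| 30% | (1 − 0.212)³ = 0.49 | (1 − 0.041)³ = 0.88 |
| 50% | (1 − 0.354)³ = 0.27 | (1 − 0.068)³ = 0.81 |
| 90% | (1 − 0.637)³ = 0.05 | (1 − 0.122)³ = 0.68 |

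**Step 2: simulation over subjects.** Assumptions: off-drug SBP mean 146, SD 10; visit SD 6; entry on a Day -7 reading above 140 and up to 165; between-subject SD of true change 4 to 8; constant effect −8; clinic SBP triggers only. Results at Day 127, where the true difference is −8:

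| Add-back share | Survivor difference (mmHg) | Placebo left of 10, about |
|---|---|---|
| 10% | about −8 | 8 |
| 30% | −7.4 to −7.7 | 5 |
| 50% | −6.8 to −7.6 | 3 |
| 90% | −5.0 to −6.6 | 1 to 2 |

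Within arms at 50 to 90% add-back, active survivors show −9.0 to −13.0 (truth −8) and placebo survivors −1.4 to −7.9 (truth 0). If the effect has gone by Day 127, active survivors still show −1.1 to −5.9. With no between-subject variation in change, the difference is essentially unbiased and mainly subjects are lost.

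**Step 3: other assumptions.** With mean 148, SD 9 and visit SD 7, a true −8 is estimated at change SD 4 and 8 as −8.0 and −8.0 (30% add-back), −7.7 and −7.0 (50%), and −6.6 and −4.8 (100%). At change SD 8, power falls from about 36% without deletion to 21%, 13% and 4%. An arm has fewer than two subjects in about 1% of trials or less at 30% add-back, 6 to 16% at 50%, and 29 to 76% at 100%.

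Diastolic and home triggers were left out of steps 1 to 3; they would lower retention.

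**The case against.** A reader might infer that the whole Post-Treatment half of the objective is lost. The documents do not support that. Days 43 and 50 fall under the 170/110 rule in 8.5.3, and the Day 64 reading normally precedes any add-back under the 140/90 rule. Three of the six Post-Treatment visits are largely untouched, provided 8.5.3 is the rule followed.

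A reader might also infer a false claim of benefit. In the runs the between-arm bias goes towards no effect, and with no true effect the survivor difference stays near zero. Add-back is discretionary, and at 10 to 30% the between-arm bias is small. This stands: the size is unknown, although at 30% about half of the placebo arm is still lost.

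The protocol synopsis says that all planned analyses compare drug with placebo, so within-arm persistence is not a planned test. That is correct, but the by-visit means will be reported and read.

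SAP 3.5.3 already compares the percentage of subjects needing antihypertensives and gives Kaplan-Meier curves for time to add-back, and SAP 3.1 has numbers of subjects in the summaries. This helps interpretation. The add-back analyses are exploratory, however, and do not repair the SBP means.

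Finally, setting aside readings taken on other antihypertensives is a recognised choice, in a small trial whose primary endpoint is AGT at Day 43. The removal alone is not the defect. The defect is a per-visit ANOVA on those left, with no stated strategy for add-back and no sensitivity analysis.

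**Conclusion.** The point holds for Days 78, 106 and 127. Followed exactly, the SAP compares outcome-selected survivors there, with unequal retention by arm whenever the drug works. The late part of the secondary SBP objective cannot be read as a comparison of the randomized groups.

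For a true −8 mmHg, the loss at Day 127 ranges from nothing at 10% add-back to about 3 mmHg at 90% (8 − 5.0 = 3.0). This rests on an assumed add-back share, SBP spread and between-subject variation in change, none of which the documents give. The loss of placebo subjects is the firmer result, since it does not need variation in change.

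That Days 43 to 64 are clean depends on 8.5.3 governing. Under the rule in protocol 3.1 and SAP 1.1, selection could begin at Day 43.

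**What to change.** 1. Reconcile the add-back rules in protocol 3.1 and SAP 1.1 with protocol 8.5.3 before treating Day 64 as the last unaffected visit. This review takes no position on which rule is right, and nothing below changes when subjects are treated.
2. In SAP 3.5.2, replace the per-visit ANOVA for SBP and DBP with one repeated-measures likelihood model over all readings up to add-back: baseline BP, arm by visit, AGT stratum and a pre-specified structured covariance. State that the clinic confirmation readings that led to add-back enter the model even if labelled unscheduled, since SAP 3.1 otherwise drops such results from by-visit summaries.
3. Label Days 78 to 127 supportive. Show the number still off therapy by arm at each visit, next to the add-back analysis of SAP 3.5.3.
4. Add a sensitivity analysis that keeps the BP collected after add-back. It answers a different question (effect regardless of added drugs) but retains the subjects removed for add-back.

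**Cost.** SAP wording, one model and one sensitivity analysis; no new data.

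**Downsides.** Late estimates lean on a missing-at-random model. With clinic triggers only, 90% add-back and change SD 8, a sequential-regression analogue of that model gave −7.6 against −5.0 for survivors, and −1.6 against −8.1 for placebo (truth 0). At 90% and change SD 4 it gained almost nothing (−6.8 against −6.7), and with no variation in change it was off by up to about 1.1 mmHg. When home readings also trigger add-back it is only partly corrective: at 50 to 90% add-back, one run gave −6.2 to −7.0, and another, with two to four home triggers per interval, −2.1 to −7.0. No accuracy to within 1 mmHg can be promised.
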